4.5 Investigator's Drug Brochure and Safety Alerts

The Investigator Drug Brochure (IDB) for everolimus is available for download from the ECOG-ACRIN webpage. The IDB provides relevant and current scientific information about the investigational product. The IDB should be submitted to your IRB/EC according to GCP regulations. The IDB and any correspondence to the Institutional Review Board (IRB)/Ethics Committee (EC) should be kept in the E2212 regulatory files.

Should any SAE report on this study qualify as a safety alert report requiring expedited reporting, the SAE report will be sent by the respective pharmaceutical company to regulatory authorities globally (including the FDA) and ECOG-ACRIN. If applicable, ECOG-ACRIN will disseminate these safety alert reports to all ECOG-ACRIN investigators in the bimonthly group mailings. These reports should be forwarded to your IRB/EC within 90 days of receipt for review. Reporting instructions are provided with each safety alert. These safety alerts and any correspondence to your IRB/EC should be maintained in your E2212 study files.

IND Status

When used in this protocol. Everolimus/placebo are each classified as an "unapproved use of an approved agent" and by definition considered investigational agents. However, while it is not an indication currently approved by the FDA, the use of everolimus/placebo in this protocol is exempt from the requirements of an IND and described under Title 21 CFR 312.2(b).

Emergency Unblinding

The information provided below is for the use by a physician, nurse, CRA or pharmacist treating the patient. These contact numbers should not be used by patients. Patients should be instructed to call their doctor's office in the event of an emergency or adverse event that may result in the need to unblind the patient.

In the event of an emergency or severe adverse reaction necessitating identification of the medication for the welfare of the patient, please contact the Study Chair, [name] M.D., at [contact] or Email [contact], first to ensure the reason for unblinding is valid. Then call a member of the ECOG-ACRIN Operations Office — Boston drug team at [contact] Monday through Friday between 9:00 AM and 5:00 PM Eastern Time. For unblinding outside of these hours, contact AnswerConnect at [name]. This service will request the reason for unblinding and then page the on-call ECOG-ACRIN staff who will return your call and provide the unblinded treatment assignment if applicable. Remember, AnswerConnect should only be contacted outside of normal business hours and only in the event of an emergency. The ECOG-ACRIN Operations Office — Boston or AnswerConnect will require the protocol number (i.e., "E2212"), the patient ID number (e.g., "44444"), and the patient initials (e.g., "FL") to unblind the patient. Note that if a patient is unblinded, he/she must discontinue protocol treatment.

Instructions for Patients Who Do Not Start Assigned Protocol Treatment

If a patient does not receive any assigned protocol treatment, baseline and follow-up data will still be collected and must be submitted through Medidata Rave according to the schedule in the E2212 Forms Completion Guidelines.

5. Treatment Plan

Administration Schedule

One cycle = 28 days.

NOTE:

Everolimus/placbo is packaged in blister cards of ten 5 mg tablets; patients should receive 6 blister cards (30 doses) for each 28 day cycle. The start of each treatment cycle may be scheduled up to 2 days later than the expected Day 1 of that cycle.

Patients should take everolimus/placebo, 10 mg, orally once daily at the same time every day, either consistently with food or consistently without food.

A missed dose may still be taken up to 6 hours after the normally scheduled time. If more than 6 hours have elapsed, patient should be instructed to skip the dose for that day. The next day, they should take everolimus/placebo at the usual time. Patients should not take 2 doses to make up for the one that they missed.

If vomiting occurs, no attempt should be made to replace the vomited dose.

Everolimus/placebo tablets should not be crushed or chewed. Tablets should be swallowed whole with a glass of water. For patients unable to swallow tablets, everolimus/placebo tablets should be dispersed completely in a glass of water (containing approximately 30 mL) by gently stirring, immediately prior to drinking. The glass should be rinsed with the same volume of water and the rinse should be completely swallowed to ensure that the entire dose is administered.

5.1.1 Treatment/ARM A

Everolimus 10 mg PO daily

Repeat cycles every 28 days for a maximum duration of 12 cycles.

5.1.2 Treatment/ARM B

Placebo PO daily

Repeat cycles every 28 days for a maximum duration of 12 cycles.

Rev. 5/14 Adverse Event Reporting Requirements

5.2.1 **Purpose**

Adverse event (AE) data collection and reporting, which are required as part of every clinical trial, are done to ensure the safety of the patients enrolled, as well as those who will enroll in future studies using similar agents.

- **Routine reporting**: Adverse events are reported in a routine manner at scheduled times during a trial using Medidata Rave.
- Expedited reporting: In addition to routine reporting, certain adverse events must be reported in an expedited manner for timelier monitoring of patient safety and care. The following sections provide information and instructions regarding expedited adverse event reporting.

5.2.2 **Terminology**

- Adverse Event (AE): Any untoward medical occurrence
 associated with the use of a drug in humans, whether or not
 considered drug related. Therefore, an AE can be ANY
 unfavorable and unintended sign (including an abnormal
 laboratory finding), symptom, or disease temporally associated
 with the use of a medicinal product, whether or not considered
 related to the medicinal product.
- Attribution: An assessment of the relationship between the adverse event and the protocol treatment, using the following categories.

ATTRIBUTION	DESCRIPTION
Unrelated	The AE is clearly NOT related to treatment.
Unlikely	The AE is doubtfully related to treatment.
Possible	The AE may be related to treatment.
Probable	The AE is likely related to treatment.
Definite	The AE is clearly related to treatment.

- CTCAE: The NCI Common Terminology Criteria for Adverse Events provides a descriptive terminology that is to be utilized for AE reporting. A grade (severity) is provided for each AE term.
- Hospitalization (or prolongation of hospitalization): For AE reporting purposes, a hospitalization is defined as an inpatient hospital stay equal to or greater than 24 hours.
- Life Threatening Adverse Event: Any AE that places the subject at immediate risk of death from the AE as it occurred.
- **Serious Adverse Event (SAE):** Any adverse event occurring at any dose that results in **ANY** of the following outcomes:
 - Death
 - A life-threatening adverse event
 - Inpatient hospitalization or prolongation of existing hospitalization (for ≥ 24 hours).
 - A persistent or significant incapacity or substantial disruption of the ability to conduct normal life functions.
 - · A congenital anomaly/birth defect.
 - Important Medical Events (IME) that may not result in death, be life threatening, or require hospitalization may be considered a serious when, based upon medical judgment, they may jeopardize the patient or subject and may require medical or surgical intervention to prevent one of the outcomes listed in this definition.

5.2.3 Reporting Procedure

This study requires that expedited adverse event reporting use CTEP's Adverse Event Reporting System (CTEP-AERS). CTEP's guidelines for CTEP-AERS can be found at http://ctep.cancer.gov. A

CTEP-AERS report must be submitted electronically to ECOG-ACRIN and the appropriate regulatory agencies via the CTEP-AERS Webbased application located at http://ctep.cancer.gov.

In the rare event when Internet connectivity is disrupted a 24-hour notification is to be made by telephone to

• the AE Team at ECOG-ACRIN [contact])

An electronic report MUST be submitted immediately upon reestablishment of internet connection.

Supporting and follow up data: Any supporting or follow up documentation must be uploaded to the Supplemental Data Folder in Medidata Rave within 48-72 hours.

NCI Technical Help Desk: For any technical questions or system problems regarding the use of the CTEP-AERS application, please contact the NCI Technical Help Desk at [contact] or by phone at [name].

5.2.4 **Determination of Reporting Requirements**

[figure not shown]
Many factors determine the reporting requirements of each individual protocol, and which events are reportable in an expeditious manner, including:

- the phase (0, 1, 2, or 3) of the trial
- whether the patient has received an investigational or commercial agent or both
- the seriousness of the event
- the Common Terminology Criteria for Adverse Events (CTCAE) grade
- whether or not hospitalization or prolongation of hospitalization was associated with the event
- when the adverse event occurred (within 30 days of the last administration of everolimus/placebo vs. ≥ 30 days after the last administration of everolimus/placebo)
- the relationship to the study treatment (attribution)

Using these factors, the instructions and tables in the following sections have been customized for protocol E2212 and outline the specific expedited adverse event reporting requirements for study E2212.

5.2.5 Steps to determine if an adverse event is to be reported in an expedited manner

5.2.5.1 Guidelines for adverse events OCCURRING WHILE ON PROTOCOL TREATMENT AND WITHIN 30 DAYS of the last administration of the everolimus/placebo.

> 5.2.5.2 Guidelines for adverse events **OCCURRING GREATER** THAN 30 DAYS after the last administration of the everolimus/placebo.

> > If the adverse event meets the definition of a **Serious** Adverse Event (SAE) as outlined by the six criteria in the top portion of the table below in Section 5.2.5.2, AND has an attribution of possible, probably or definite, the following events require reporting as follows:

Expedited 24-hour notification followed by complete report within 5 calendar days for:

All Grade 4 and 5 adverse events

NOTE: Any death occurring greater than 30 days after the last dose of investigational agent with an attribution of possible, probable or definite must be reported via CTEP-AERS even if the patient

is off study.

Expedited 10 calendar day reports for:

- Grade 2 adverse events resulting in hospitalization or prolongation of hospitalization
- Grade 3 adverse events

Expedited Reporting Requirements for Arm X (Arm A or B) on 5.2.6 **Protocol E2212**

Investigational Agents: Everolimus/Placebo

Commercial Agents: None

NOTE: Although the agents used on this protocol are IND exempt,

the adverse event investigational reporting requirements

will be used on this protocol.

Late Phase 2 and Phase 3 Studies

Expedited Reporting Requirements for Adverse Events that Occur on Studies under an IND within 30 Days of the Last Administration of the Investigational Agent/Intervention.1

NOTE: Footnote 1 instructs how to report serious adverse events that occur more than 30 days after the last administration

of investigational agent/intervention.

Rev. 5/14

Rev. 5/14

REPORTING REQUIREMENTS FOR SERIOUS ADVERSE EVENTS (21 CFR Part 312)

NOTE: Investigators MUST immediately report to the sponsor (NCI) ANY Serious Adverse Events, whether or not they are considered related to the investigational agent(s)/intervention (21 CFR 312.64)

An adverse event is considered serious if it results in **ANY** of the following outcomes:

- 1. Death
- 2. A life-threatening adverse event
- 3. An adverse event that results in inpatient hospitalization or prolongation of existing hospitalization for ≥ 24 hours
- 4. A persistent or significant incapacity or substantial disruption of the ability to conduct normal life functions
- 5. A congenital anomaly/birth defect.
- 6. Important Medical Events (IME) that may not result in death, be life threatening, or require hospitalization may be considered serious when, based upon medical judgment, they may jeopardize the patient or subject and may require medical or surgical intervention to prevent one of the outcomes listed in this definition. (FDA, 21 CFR 312.32; ICH E2A and ICH E6).

ALL SERIOUS adverse events that meet the above criteria MUST be immediately reported to the NCI via CTEP-AERS within the timeframes detailed in the table below.

Hospitalization	Grade 1 Timeframes	Grade 2 Timeframes	Grade 3 Timeframes	Grade 4 & 5 Timeframes
Resulting in Hospitalization ≥ 24 hrs	10 Calendar Days			24-Hour 5 Calendar
Not resulting in Hospitalization ≥ 24 hrs	Not required		10 Calendar Days	Days

Expedited AE reporting timelines are defined as:

- "24-Hour; 5 Calendar Days" The AE must initially be reported via CTEP-AERS within 24 hours of learning of the AE, followed by a complete expedited report within 5 calendar days of the initial 24-hour report.
- "10 Calendar Days" A complete expedited report on the AE must be submitted within 10 calendar days of learning of the AE.

Expedited 24-hour notification followed by complete report within 5 calendar days for:

• All Grade 4, and Grade 5 AEs

Expedited 10 calendar day reports for:

- Grade 2 adverse events resulting in hospitalization or prolongation of hospitalization
- · Grade 3 adverse events

5.2.7 Additional instructions, requirements and exceptions for protocol E2212

Additional Instructions:

For instructions on how to specifically report events that result in persistent or significant disability/incapacity, congenital anomaly, or birth defect events via CTEP-AERS, please contact the AEMD Help Desk at [contact] or [contact]. This will need to be discussed on a case-by-case basis.

E2212 specific expedited reporting requirements:

Pregnancy

Pregnancies and suspected pregnancies (including a positive or inconclusive pregnancy test regardless of age or disease state)

¹ Serious adverse events that occur more than 30 days after the last administration of investigational agent/intervention and have an attribution of possible, probable, or definite require reporting as follows:

occurring while the subject is on Everolimus/Placebo, or within 28 days of the subject's last dose of Everolimus/Placebo, are considered immediately reportable events. The pregnancy, suspected pregnancy, or positive/inconclusive pregnancy test must be reported via CTEP-AERS within 24 hours of the Investigator's knowledge.

Please refer to Appendix VI for detailed instructions on how to the occurrence of a pregnancy as well as the outcome of all pregnancies.

5.2.8 Other recipients of adverse event reports and supplemental data

ECOG-ACRIN will forward CTEP-AERS reports to the appropriate regulatory agencies and Novartis within 24 hours of receipt.

A drug supporter representative may call a site for additional or supplemental information regarding a serious adverse event. Any additional written AE information requested by the drug supporter MUST be submitted to BOTH ECOG-ACRIN and the drug supporter.

Adverse events determined to be reportable via CTEP-AERS must also be reported by the institution, according to the local policy and procedures, to the Institutional Review Board responsible for oversight of the patient.

5.2.9 Second Primary Cancer Reporting Requirements

All cases of second primary cancers, including acute myeloid leukemia (AML) and myelodysplastic syndrome (MDS), that occur following treatment on NCI-sponsored trials must be reported to ECOG-ACRIN using Medidata Rave

- A second malignancy is a cancer that is UNRELATED to any prior anti-cancer treatment (including the treatment on this protocol). Second malignancies require ONLY routine reporting as follows:
 - 1. Complete a Second Primary Form in Medidata Rave within 14 days.
 - 2. Upload a copy of the pathology report to ECOG-ACRIN via Medidata Rave confirming the diagnosis.
 - If the patient has been diagnosed with AML/MDS, upload a copy of the cytogenetics report (if available) to ECOG-ACRIN via Medidata Rave.
- A secondary malignancy is a cancer CAUSED BY any prior anticancer treatment (including the treatment on this protocol).
 Secondary malignancies require both routine and expedited reporting as follows:
 - Complete a Second Primary Form in Medidata Rave within 14 days.
 - 2. Report the diagnosis via CTEP-AERS at http://ctep.cancer.gov

- Report under a.) leukemia secondary to oncology chemotherapy, b.) myelodysplastic syndrome, or c.) treatment related secondary malignancy.
- Upload a copy of the pathology report to ECOG-ACRIN via Medidata Rave and submit a copy to NCI/CTEP confirming the diagnosis.
- If the patient has been diagnosed with AML/MDS, upload a copy of the cytogenetics report (if available) to ECOG-ACRIN via Medidata Rave and submit a copy to NCI/CTEP.

NOTE: The Second Primary Form and the CTEP-AERS report should not be used to report recurrence or development of metastatic disease.

NOTE: If a patient has been enrolled in more than one NCI-sponsored study, the Second Primary Form must be submitted for the most recent trial. ECOG-ACRIN must be provided with a copy of the form and the associated pathology report and cytogenetics report (if available) even if ECOG-ACRIN was not the patient's most recent trial.

NOTE: Once data regarding survival and remission status are no longer required by the protocol, no follow-up data should be submitted via CTEP-AERS or by the Second Primary Form.

Dose Modifications

5.3.1 General

If dose reduction is required, reduction is permanent. Missed doses may be taken up to 6 hours after normally scheduled time. If more than 6 hours have elapsed, patient should be instructed to skip the dose for that day. The next day, they should take everolimus/placebo at the usual time. Patients should not take 2 doses to make up for the one that they missed.

If multiple toxicities are seen, the dose administered in a subsequent cycle should be based on the most severe toxicity experienced in the current cycle.

AEs determined to be unrelated to study treatment will not require dose reduction.

If everolimus/placebo is held for > 4 weeks (28 days), patient must discontinue protocol treatment.

All toxicities should be graded according to the Common Terminology Criteria for Adverse Events (version 4.0).

All appropriate treatment areas should have access to a copy of the CTCAE version 4.0. A copy of the CTCAE version 4.0 can be downloaded from the CTEP website (http://ctep.cancer.gov).

5.3.2 Everolimus/Placebo Dose Modifications

 For individual subjects, dose modifications will be based on hematologic or non-hematologic toxicity, laboratory test results,

- and clinical assessment on the day of treatment and during the previous cycle.
- If dose delays are required, weekly evaluation with laboratory tests and clinical assessments, if applicable, should be performed until recovery to the specified grade or until the subject is discontinued from the study.
- If toxicities have not resolved within ≤ 4 weeks (28 days), patient must discontinue protocol treatment.
- The study chair or study chair liaison should be contacted for dose delays and modifications for all other toxicities not listed in this section.
- One dose reduction is permitted before everolimus/placebo will be discontinued. Patients who require further dose reductions beyond the -1 dose level must be discontinued from study treatment.

Everolimus/Placebo Dose Level Table			
Dose Level	Dose in mg		
0	10 mg daily		
-1	5 mg daily		

5.3.2.1 Management of Hematologic Toxicity

Toxicity	Action
Grade 2 Platelet count decreased	No action
Grade 3 Platelet count decreased	Interrupt everolimus/placebo until resolution to grade ≤ 1 If resolution occurs ≤ 7 days, reintroduce everolimus/placebo at the dose level prior to interruption.
	If resolution occurs > 7 days, or event occurs within 28 days, reintroduce everolimus/placebo at one dose level lower, if available.
Grade 4 Platelet count decreased	Interrupt everolimus/placebo until recovery to grade ≤ 1. Then reintroduce everolimus/placebo at one dose level lower, if available.
Grade 3 Neutrophil count decreased	Interrupt everolimus/placebo until resolution to grade ≤ 1 or baseline value
	If AE resolution occurs ≤ 7 days, reintroduce everolimus/placebo at the same dose level.
	If AE resolution occurs > 7 days, or event occurs within 28 days, reintroduce everolimus/placebo at one dose level lower, if available.
Grade 4 Neutrophil count decreased or grade 4 Anemia	Interrupt everolimus/placebo until recovery to grade ≤ 1 or baseline value. Reintroduce everolimus/placebo at one dose level lower, if available.
Febrile neutropenia	Interrupt everolimus/placebo until resolution to grade ≤ 1 (or baseline value) and no fever. Reintroduce everolimus/placebo at one dose level lower, if available.
Recurrence of grade 3 hematologic toxicity after dose reduction	Reduce dose to the next lower dose level, if available.

Recurrence of grade 4 hematologic toxicity (including febrile neutropenia) after dose reduction	Discontinue protocol treatment.
Any hematologic toxicity requiring everolimus/placebo interruption for > 28 days	Discontinue protocol treatment.

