5.3.2.2 Non-Hematologic Toxicity

Toxicity	Action
AST or ALT elevation Grade 1 (> ULN - 3.0 x ULN) Grade 2 (> 3.0 - 5.0 x ULN)	Maintain current dose level
AST or ALT elevation Grade 3 (> 5.0 - 20.0 ULN)	Interrupt everolimus/placebo administration until resolution to ≤ grade 1 (or ≤ grade 2 if baseline values were within the range of grade 2). If resolution occurs ≤ 7 days, everolimus/placebo should be re-started at the dose level prior to interruption.
	If resolution takes > 7 days, or if event recurs within 28 days, hold everolimus/placebo until recovery to ≤ grade 1 or baseline grade / value and reintroduce everolimus/placebo at one dose level lower, if available.
AST or ALT elevation Grade 4 (> 20 x ULN)	Interrupt everolimus/placebo administration until resolution to ≤ grade 1 (or ≤ grade 2 if baseline values were within the range of grade 2). If resolution occurs ≤ 7 days, everolimus/placebo should be re-started at one dose level lower. If resolution takes > 7 days, discontinue everolimus/placebo.
Intolerable grade 3 AE, except hyperglycemia or	Interrupt everolimus/placebo administration until resolution to ≤ grade 1 or baseline grade / value.
hypertriglyceridemia or hypercholesterolemia	If resolution occurs within ≤ 7 days, everolimus/placebo should be re-started at the dose level prior to interruption.
	If resolution takes > 7 days, or if event recurs within 28 days, hold everolimus/placebo until recovery to ≤ grade 1 or baseline grade / value and reintroduce everolimus/placebo at one dose level lower, if available.
	Patients will be withdrawn from the study if they fail to recover to ≤ grade 1 or baseline grade / value within 28 days.
Any other grade 4 non- hematologic	Hold everolimus/placebo until recovery to grade ≤ 1 or baseline value
, and the second	Reintroduce everolimus/placebo at one dose level lower, if available.
Grade 3 or 4 clinical liver failure (asterixis or encephalopathy/coma)	Discontinue everolimus/placebo
Recurrence of intolerable grade 2 mucositis or grade 3 event after dose reduction	Reduce dose to the next lower dose level, if available.
Recurrence of grade 4 non- hematologic toxicity after dose reduction	Discontinue protocol treatment.
Any non-hematologic toxicity requiring Everolimus/Placebo interruption for > 28 days	Discontinue protocol treatment.

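### The grade 3 platelet and neutrophil rows say an event *occurs* within 28 days where parallel rows say *recurs*, so a brief first drop can meet two rules that give different doses.

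*Combined protocol and SAP*

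**What the plan says.** Section 5.3.2.1 gives two restart rules for a grade 3 fall in platelets once it has resolved. The first is "If resolution occurs ≤ 7 days, reintroduce everolimus/placebo at the dose level prior to interruption". The second, which orders a restart one level down, begins "If resolution occurs > 7 days, or event occurs within 28 days".

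The grade 3 neutrophil row has the same pair in slightly different words: "If AE resolution occurs ≤ 7 days, reintroduce everolimus/placebo at the same dose level", then "If AE resolution occurs > 7 days, or event occurs within 28 days" for the lower dose.

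A later row of the same table deals with repeat events and names them as such: "Recurrence of grade 3 hematologic toxicity after dose reduction".

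In section 5.3.2.2, the rows for grade 3 AST/ALT elevation and for intolerable grade 3 events use the same two-part structure, but the second part reads "If resolution takes > 7 days, or if event recurs within 28 days".

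Section 5.3.1 adds "If dose reduction is required, reduction is permanent" and limits the scope with "AEs determined to be unrelated to study treatment will not require dose reduction". Section 5.3.2 allows a single reduction, from 10 mg to 5 mg daily, and requires study treatment to stop in anyone who needs to go lower.

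**The concern.** The two sentences in each blood-count row are meant to separate events that return to full dose from events that lead to a cut. With *recurs*, they do. With *occurs* and no starting point for the 28 days, a site may count from first dose or from Day 1 of the cycle. A first drop that clears in, say, 4 days can then fall under both sentences, one ordering 10 mg and the other 5 mg.

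Because a reduction cannot be reversed and only one is allowed, choosing the wrong sentence has lasting consequences for that patient. Two sites could dose the same event differently.

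The wording can also err the other way. If a site counts from first dose, a patient with repeated grade 3 drops after day 28, each clearing within 7 days, never meets the cut rule and restarts at 10 mg every time. The *recurs* wording would reduce the dose when a repeat falls within 28 days.

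**Working it through.** The plan states no figure to reproduce here. The check compares the text of the rules and then steps through a patient.

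**1. Wording of the four grade 3 rows that share this structure**

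| Row | Section | Second trigger for a cut |
|---|---|---|
| Platelets | 5.3.2.1 | *occurs* within 28 days |
| Neutrophils | 5.3.2.1 | *occurs* within 28 days |
| AST/ALT | 5.3.2.2 | *recurs* within 28 days |
| Intolerable grade 3 event | 5.3.2.2 | *recurs* within 28 days |

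The two *occurs* rows are worded differently from each other elsewhere, so an error in reading the PDF is an unlikely explanation.

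**2. Does another rule settle it?** No.
- Sections 5.3.1 and 5.3.2 give no order of precedence.
- The instruction in 5.3.2 to contact the study chair covers toxicities that the section does not list; these two are listed.
- The recurrence rows of the 5.3.2.1 table apply only after a reduction has been made, so they do not govern the first cut.

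**3. A first grade 3 event under the literal text**
- Resolves in ≤ 7 days, inside the window: both rules are met.
- Resolves in ≤ 7 days, outside the window: same dose only.
- Resolves in > 7 days: cut only.

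With *recurs*, the first case becomes same dose only.

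**4. How wide the window is for a first event.** Planned treatment is 12 cycles × 28 days = 336 days (sections 5.1.1 and 5.1.2). The starting points below are assumptions, since the plan gives none.
- From first onset or restart, in the *recurs* sense: no first event falls in the window.
- From first dose: 28/336 = 8.3% of planned treatment days.
- From Day 1 of the current cycle: 28/28 = 100%, or 28/30 = 93% if the next cycle starts 2 days late, as section 5 permits.

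These are shares of treatment days, not of events. On the last count the ≤ 7-day rule would be almost empty, which is further evidence that *recurs* was meant.

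**5. Step-through.** Assume every drop is grade 3 and drug-related, resolves in ≤ 7 days, and is followed by the next within 28 days.

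| Drop | Dose-cut reading | *Recurs* reading |
|---|---|---|
| 1 | 10 mg to 5 mg | back to 10 mg |
| 2 | no lower level: discontinue | 10 mg to 5 mg |
| 3 | – | no lower level: discontinue |

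The cut is (10 − 5)/10 = 50%. If repeats come more than 28 days apart, discontinuation on the *recurs* reading comes later still.

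**The case against.** The strongest reply is that context makes the meaning plain. The row runs in sequence: interrupt, restart at the same dose if recovery is quick, go lower if it is slow or if there is an event within 28 days. Read that way, the last clause means a repeat, as the next table says outright. Many sites would probably infer this. It is a reason to call the problem a wording slip rather than a chosen rule, but the text still does not say it, and a dosing table should not depend on inference.

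It can also be said that, if 28 days are counted from first dose, the clause works as an exception for early events and need not collide with the ≤ 7-day rule. That is a possible reading, but the table does not present the clause as an exception.

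Three further points stand as limits.
- The window shares rest on starting points supplied by the reader and say nothing about how many patients are affected.
- Discontinuation follows from combining two provisions: the 5.3.2.1 row on recurrence after reduction asks for a lower level only where one exists, and section 5.3.2 then requires stopping.
- Both arms use the same blinded table and the primary analysis includes all randomized eligible patients, so the validity of the test is not in question.

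The argument that a misreading only errs toward less exposure does not stand: counting from first dose can also leave repeated later drops at full dose.

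**Conclusion.** The concern holds. In two rows of an operative dosing table, a brief first grade 3 drop can literally meet both the same-dose rule and the dose-cut rule, and nothing in the plan resolves the conflict. For a patient dosed on the cut reading, the effect is a permanent 50% reduction, loss of the only permitted step, and discontinuation at the second grade 3 drop instead of the third at the earliest. This assumes drug-related drops with the timing used in the step-through.

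The textual mismatch is certain; the practical harm cannot be sized. Section 8.1.13.12 lists thrombocytopenia and neutropenia as side effects without rates. It is reasonable to expect inconsistent handling to fall more on the everolimus arm, but no number can be put on that. Sample size, power and type I error are untouched. This is a correction that should be made, not a threat to the trial.

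**What to change.** In the grade 3 platelet row and the grade 3 neutrophil row of section 5.3.2.1, replace *occurs* with *recurs* in the 28-day clause. That alone removes the conflict. Preferably also state that the 28 days run from the restart of everolimus/placebo. The plan does not itself favour restart over first onset, so this is the sponsor's choice. The same starting point could be added to the two matching rows of section 5.3.2.2 for clarity, although no rules conflict there.

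The cost is one word in each of two rows, plus an optional phrase, by protocol amendment. Sample size, visit schedule and data collection do not change.
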